5.0 Methods

The proposed study will be completed on 9cc in Wake Forest Baptist Health. Study subjects will be recruited on 9cc in Wake Forest Baptist Health after approval from the treating physician. Recruitment, consent, and data collection will be completed in the privacy of the patient's room.

The nature, purpose, and risks of all procedures and protocols will be explained to each participant prior to obtaining written consent. All examiners are trained in the standardized conduction of all assessments before data collection. Standardized written instructions will be provided.

Subjects will not be recruited for the observational study cohort as this cohort is closed to enrollment.

Enrollment will be limited to the additional the expanded **HIIT Cohort (n= 22)**. Using random number generator, eligible patients will be randomized into two groups: Group 1, Continuous Ambulation (n = 12), and Group 2, Interval Ambulation (n =10). Assignment will be provided by the study coordinator. The study PI will be blinded to this randomization.

Provider participants will be enrolled if they are caring for patients on 9cc during the study period.

5.1a Study timeline (Observational Cohort)

	Initial Visit	Day 1	Day 2	Day 3
Informed Consent	X			
Medical Record Review	X			
Vital Signs	X	X	X	X
Walking Assessment		X	X	X
Fatigue Assessment		X	X	X
Pain Assessment		X	X	X
Walking Distance Measurement		X	X	X
Step/Pedometer Evaluation ¹		X	X	X

Feasibility Assessment of the Wake Forest Real-time Tracking System for Monitoring
Patient Movement during Postoperative Recovery: Part 2
IRB 00039439

Distribution of SPOT Badge	X			
Physical Activity in Hospital Survey				X

¹ Patients will wear a Fitbit Zip™ and Kenz Lifecorder EX Accelerometer for pedometer evaluation.

5.1b Study timeline (HIIT Cohort)

	Initial Visit	Ambulatory Evaluation
Informed Consent	X	
Medical Record Review	X	
Vital Signs	X	X
Walking Assessment		X
Grip Assessment		X
Pedometer Evaluation ¹		X
Distribution of SPOT Badge ²	na	
Patient Survey		X

¹ Patients will wear a Kenz Lifecorder EX Accelerometer for pedometer evaluation during walking assessment.

² SPOT badges are now worn by all inpatients at WFBH and no longer require badging specifically for this project.

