5.6 Walking Assessment and Physical Activity Survey (Observational Cohort)

All participants will receive a visit by a study team member each day for maximum of 3 days. If discharge is less than 24 hours after enrollment, the participant will be excluded from study. Study participants will be invited by a study team member to join them on a walk. Time, distance, and duration will be determined by the patient. If nursing staff or treating provider determines that walking is not safe or inappropriate, walk will not be performed and rationale documented. If patient declines to walk, rationale will be documented. For all patients who decline, a second visit by a study team member will occur later in the day. Participants will be encouraged to walk by study team members emphasizing the importance of walking after surgery. Each participant will complete a pre- and post-walk assessment including measurement of pain and fatigue. Pre- and post-walk vital signs will be recorded. Participants will also be asked to report number of walks completed in the last 24 hours along with distance traveled. At completion of walk, the study team will record exact time of walk, distance, and duration. At conclusion of walk assessment, the patient will complete a physical activity in hospital survey. Survey data will be collected in the subject's private room.

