5.7.4 Ambulatory Session

Each subject perform one ambulatory session during the study. This will include walking 40 meters. Gait speed will be calculated using the speed

Feasibility Assessment of the Wake Forest Real-time Tracking System for Monitoring Patient Movement during Postoperative Recovery: Part 2
IRB 00039439

in which the subject walked 40 meters. Alternative exercise (hand bike) will be provided if subject declines ambulation or unable to ambulate out of their room. Demonstration of the hand bike will be provided by the study team member and subjects will be allowed to practice with the bike prior to exercise session. For subjects unable to perform the ambulatory session, a study team member will return on a subsequent hospital day to complete this portion of the study. If patient unable to perform the ambulatory session during their hospitalization or during the study period, the reason will be documented.

1. Walking Continuous Training (Group 1): The total distance will be 40 meters. Study team members will walk, support, and coach the subject to walk as slow as he/she wants.
2. Walking Interval Training (Group 2): The subject will walk a total distance of 40 meters. This distance will be divided into four intervals of 10 meters to equal the same measured distance as the continuous group. The subject will receive two minutes of rest between each interval and will be supported and coached to walk as fast as they can.
3. Hand Bike Continuous Training (Group 1, alternative option until able to participate in ambulatory session): The subject will be asked to bike for 5 minutes continuously with coaching “go as slow as you want.”
4. Hand Bike Interval Training (Group 2, alternative option until able to participate in ambulatory session): The subject will be asked to bike in 10 second intervals (“as fast as they want to go”) and rest for 50 seconds for five rounds (i.e. every minute on the minute (EMOM)).

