The study team will also capture information from this pilot study that will be used to improve the efficiency of larger studies. We will evaluate the capabilities of the SPOT system to monitor patient movement. Feasible study will be defined as more than 80% of badges assigned to the observational study participants will detect movement in and out a room. All data will be descriptive in nature and will focus on patterns of movement and presence or absence of data. Summary statistics such as means and standard deviations will be calculated for continuous measures and counts and percentages will be calculated for discrete measures. Agreement statistics, including kappa statistics, sensitivity, and specificity, will be calculated. Changes of pre- and post- vital signs will be calculated and graphical display will be performed to show the changes over time. The correlation between walking distance as well as pain and fatigue will be calculated each day. Mixed effects models will be used to study the association over time. Since the sample size is small, we are aware that the models may not be stable. Thus, descriptive analysis will be our primary analysis.

The additional HITT study cohort will enable validation of SPOT system to capture out of room events under various ambulatory patterns. This will build on the current cohort that validated simple in and out of room events. Feasible study will be defined as more than 80% of badges assigned to participants detect movement in and out a room during continuous and interval movement patterns.

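### The HIIT 80% feasibility rule is written over all assigned badges, so read literally a subject with no exit counts as a missed exit, and it does not say whether the groups are pooled

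*Combined protocol and SAP*

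**What the plan says.** Primary outcome 6.1 is whether SPOT can detect a patient's movement into and out of the room. Outcome 6.2.6 asks whether detection holds when the patient varies how they walk. Section 7.2 says the HIIT cohort was added to validate the system under such patterns.

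Section 7.2 sets two criteria:

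- Observational cohort (40 patients): "more than 80% of badges assigned to the observational study participants will detect movement in and out a room".
- HIIT cohort (12 continuous, 10 interval): "more than 80% of badges assigned to participants detect movement in and out a room during continuous and interval movement patterns".

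Neither criterion says what happens to a patient with no exit. The plan foresees such patients:

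- Section 5.7.4 (HIIT): "Alternative exercise (hand bike) will be provided if subject declines ambulation or unable to ambulate out of their room". A team member returns on a later day, but "If patient unable to perform the ambulatory session during their hospitalization or during the study period, the reason will be documented".
- Section 5.6 (observational): "If patient declines to walk, rationale will be documented", after which a second visit follows the same day. Walks may also be held back by clinical staff.

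Section 7.2 also plans kappa, sensitivity and specificity, and makes descriptive analysis primary. It does not link those statistics to the 80% criteria.

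**The concern.** A badge can register an exit only if the patient leaves the room. With every assigned badge in the denominator, the verdict mixes two things: whether patients left the room, and whether the system saw them when they did. Outcome 6.1 asks only about the second. A HIIT subject who used only the hand bike, or never did the session, would score the same as a missed exit.

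The second gap is pooling. The HIIT criterion names both movement patterns but does not say whether more than 80% is required of all 22 subjects or of each group. Poor detection during interval walking is what the cohort was added to reveal, and a pooled percentage can hide it.

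At stake is how the result is read when larger studies are planned: a fail that reflects immobility, or a pooled pass that conceals weak interval detection.

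**Working it through.** **The plan's own figure.** Section 7.1 states more than 90% power with 20 subjects, null 0, alternative 0.9 and prevalence 0.3. That gives 20 × 0.3 = 6 positives. With a null of 0, one detection rejects, so power is 1 − 0.1^6 = 0.999999. At prevalence 0.1 there are 2 positives and power is 1 − 0.1^2 = 0.99. The figure reproduces when the number of positives is taken as fixed, but it does not involve the 80% rule. The plan gives no operating characteristics for that rule.

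**Thresholds implied by more than 80%.**

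- Observational: 32/40 = 80.0% fails, so 33/40 is needed.
- HIIT pooled: 17/22 = 77.3% fails, so 18/22 (81.8%) is needed.
- HIIT per group: 10/12 (83.3%) and, because 8/10 is exactly 80%, 9/10.

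**Perfect detection.** With 5 non-exiters, HIIT reaches 17/22 and fails; with 4 it reaches 18/22 and passes. In the observational cohort, 8 non-exiters give 32/40 and fail; 7 give 33/40 and pass.

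The documents give no non-exit rate. For assumed rates q, the chance that a perfect system passes is P(X ≥ r), with X binomial (n, 1 − q):

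| q | n = 40, r = 33 | n = 22, r = 18 |
|---|---|---|
| 5% | 0.999 | 0.996 |
| 10% | 0.96 | 0.94 |
| 15% | 0.76 | 0.77 |
| 20% | 0.44 | 0.54 |

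**Imperfect detection, HIIT pooled.** With m non-exiters and detection probability s per session, the pass probability is P(X ≥ 18), X binomial (22 − m, s). The value 0.9 is the alternative in section 7.1, taken here as per-session detection. The value 0.98 is an assumption, chosen near the almost 100% that section 7.1 reports from preliminary tests.

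| m | s = 0.9 | s = 0.98 |
|---|---|---|
| 0 | 0.94 | 1.00 |
| 2 | 0.68 | 0.99 |
| 3 | 0.42 | 0.95 |

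With 2 non-exiters the nominal 80% bar becomes 18/20 = 90% of those who had an exit to detect.

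**Pooling.** 12/12 plus 6/10 is 18/22, a pass, with interval detection at 60%. As a stress case, take perfect continuous detection and a true interval detection of 0.6. The pooled rule passes with P(X ≥ 6 | 10, 0.6) = 0.63. If the interval group had to exceed 80% itself, the chance is P(X ≥ 9 | 10, 0.6) = 0.05. The opposite cost: at 0.9 detection in both groups, requiring each to pass gives 0.889 × 0.736 = 0.65, against 0.94 pooled.

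**The case against.** **A fair reading may exclude non-walkers.** The HIIT criterion speaks of detection during the two movement patterns, and a subject who never walked produced neither. That reading is open. It is not written, however, and the stated denominator is still assigned badges. This is therefore an ambiguity with a literal consequence, not an established rule that non-exiters fail.

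**Few patients will have no exit.** Exclusion 4.2.4 removes patients who cannot or may not walk, 4.2.6 removes some with complications, and both cohorts allow further attempts. Declining a staff walk is not the same as staying in the room: observational badges record continuously, and "Participants will also be asked to report number of walks completed in the last 24 hours along with distance traveled". This stands. At 5% non-exit or less a perfect system almost always passes.

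**An all-assigned denominator is a recognisable conservative choice.** It keeps badge-wear and positioning problems in the result and errs towards failing. That is a reason to report it, but it still does not answer outcome 6.1 by itself.

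**Agreement statistics are planned, and the pilot is descriptive.** Sensitivity would show a poor system even if the verdict did not, and no passage attaches a go/no-go decision to the 80% figure. This lowers the severity.

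**Stronger readings that a reader might infer:**

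- That the observational rule lets a poor system pass, because no walk, window or number of detections is named. With 50% detection, three trips per patient and independent misses (all assumed), one badge succeeds with probability 1 − 0.75^3 = 0.58 if exit and entry must be seen on the same trip, or (1 − 0.5^3)^2 = 0.77 if on any trips. The chance of 33 or more of 40 is then 0.0008 or 0.25. More trips (0.58 to 1.00 at six) or looser definitions raise it, but the documents give no trip count and the cohort is closed.
- That section 5.5 and the HIIT timeline contradict each other on who provides badges. The timeline footnote explains the change: "SPOT badges are now worn by all inpatients at WFBH and no longer require badging specifically for this project". Section 5.5 may be text carried over from the observational cohort.
- That the HIIT session might never cross the doorway. Section 7.2 describes the cohort as testing out-of-room events. The last two points are missing detail, not errors.

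**Conclusion.** The point holds mainly for HIIT, in two parts: the denominator for sessions never performed, and pooled versus per-group judgement. Read literally, 5 of 22 non-exiters fail a perfect system. At 0.9 detection, 2 or 3 non-exiters already bring the pass probability down to 0.68 or 0.42. If detection is near 0.98 and non-exit is rare, the effect is small. The non-exit counts, the 0.98 and the 60% interval detection are all assumptions.

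The observational rule has the same denominator flaw (8 of 40), but enrollment there is closed and section 7.2 already speaks of that cohort as having validated simple room events. Only the reporting can change.

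The documents do not support the conclusion that the study cannot validate SPOT or that its verdict will be wrong. The finding is that a stated rule should be made to answer its stated question. For a descriptive pilot with agreement statistics already planned, this is of lower severity than a required correction.

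**What to change.** **HIIT, set in advance in section 7.2.**

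- Denominator: subjects with a staff-observed out-of-room session.
- Numerator: those among them whose badge shows a matching out-of-room event, within a stated time window.
- Keep the 80% threshold and state that it is judged pooled. Report detection by group as well, with exact 95% CIs, so that poor interval detection is visible.
- List subjects with no observed exit separately, with reasons.

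**Observational cohort.** Keep the plan's badge percentage. Beside it, labelled as a revised descriptive analysis with no new threshold, give the proportion detected among staff-accompanied out-of-room walks, with a patient-clustered 95% CI. The reference data exist: "At completion of walk, the study team will record exact time of walk, distance, and duration".

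**Cost.** A few sentences of wording, plus timestamp matching. HIIT may need one added field for session clock times, since sections 5.7.4 and 5.7.6 imply only elapsed time. The HIIT denominator shrinks as non-exiters leave it, and intervals are wide in any case: 18/22 has an exact 95% CI of 60% to 95%. The observational addition is post hoc and must be labelled so.

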5.5 SPOT/RTLS Badges and Data

All participants will wear a SPOT badge provided by the study team throughout the study period. Research staff will stress that participants should wear the pedometer during the study period. Participants will be asked to wear the activity monitors at all times except while bathing or showering. SPOT badge data is collected continuously by the SPOT team independent of the study team. This is standard procedures for Wake Forest Baptist Health. The study team will coordinate with the SPOT team to extract data specific for this study. The extracted data will be stored in secure, password-protect files behind the WFBH firewall using excel files.

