7.0 Analytic Plan

7.1 Sample size

40 subjects will be included in initial observational study. Preliminary tests of SPOT badges indicate sensitivity and specificity nearly 100% using controlled movements on 9cc. Assuming type I error of 0.05, a two-sided test, 20 subjects, the sensitivity or specificity under the null equal to 0, and prevalence of 0.3, we have more than 90% power to detect the sensitivity of specificity under the alternative hypothesis equal to 0.9. If we use a range of prevalence from 0.1 to 0.9, we still have more than 90% power. However, the positioning of SPOT badge may decrease the sensitivity and specificity of the movement readings. Review of preliminary survey data indicates significant variability in response indicating need for expansion of sample size for secondary study objectives. With 40 subjects being recruited, we will be sure to have enough power to demonstrate the feasibility of this study and provide appropriate confidence intervals for future studies.

For provider participants, a maximum of 50 respondents will be included in the study. Based on staffing, resource demands, and learner rotations, the exact number of respondents available may be lower than 50 respondents. With 50 subjects being recruited, we will be sure to have

Feasibility Assessment of the Wake Forest Real-time Tracking System for Monitoring Patient Movement during Postoperative Recovery: Part 2
IRB 00039439

enough power to demonstrate the feasibility of exercise and patient mobility monitoring programs. This number will also provide appropriate confidence intervals for future studies.

For the additional HITT cohort, we will enroll a maximum of 22 subjects. This sample size will have sufficient power to demonstrate the feasibility of this study and provide appropriate confidence intervals for future studies.

In total, targeted study enrollment will be 62 patients and 50 providers.

7.2 Feasibility analysis and statistics.

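### The only feasibility rule in 7.2 scores each badge yes or no without saying what share of exits it must detect, so the same 80% can mean very different standards in the two cohorts

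*Combined protocol and SAP*

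**What the plan says.** Section 7.2 of the combined protocol and SAP has one success rule per cohort.

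- Observational: "more than 80% of badges assigned to the observational study participants will detect movement in and out a room".
- HIIT: "more than 80% of badges assigned to participants detect movement in and out a room during continuous and interval movement patterns".

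The unit is the badge. Neither rule gives a number or share of exits to be detected. Section 7.2 also plans kappa, sensitivity and specificity, but with no threshold and no unit of analysis, so they do not enter the feasibility decision. It says the data will centre on patterns of movement and on whether data are present or absent, and that the HIIT cohort extends what the observational cohort validated.

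Exposure differs between the cohorts:

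- Section 5.6: "All participants will receive a visit by a study team member each day for maximum of 3 days". Walks may be declined or ruled out by clinical staff.
- Section 5.5: "SPOT badge data is collected continuously by the SPOT team independent of the study team". Exits outside the escorted walk are therefore logged too.
- Section 5.7.4: "Each subject perform one ambulatory session during the study". An in-room hand bike is the alternative until the patient can walk. The number of room crossings per session is not given.

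On size, section 7.1 states "40 subjects will be included in initial observational study" and "For the additional HITT cohort, we will enroll a maximum of 22 subjects".

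**The concern.** Monitoring movement requires a system that catches most exits. A badge that logs one exit and misses the rest satisfies the rule on its plainest reading, and the more often a patient leaves the room, the easier the badge passes. A pass could then support a feasibility conclusion that the exit-level data do not.

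The second problem is the shared 80%. If observational badges have several chances and HIIT badges one, an identical system can pass the first rule and fail the second. Outcome 6.2.6 asks whether detection survives a change in walking pattern, so a HIIT failure of that kind could be mistaken for an effect of the pattern.

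**Working it through.** **The plan's own figure.** Section 7.1 claims more than 90% power with 20 subjects, prevalence 0.3, sensitivity 0 under the null and 0.9 under the alternative. That gives 20 × 0.3 = 6 positives. With a null of 0, a single detection rejects, so power is 1 − 0.1^6 = 0.999999. At prevalence 0.1 there are 2 positives and power is 1 − 0.1² = 0.99. With the number of positives fixed this way, the claim reproduces. It says nothing about the 80% rule, for which the plan gives no operating characteristics.

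**Thresholds.** 80% of 40 is 32, so more than 80% means at least 33 of 40. 80% of 22 is 17.6, so at least 18 of 22 if HIIT is pooled. Section 7.2 does not say whether HIIT is pooled or judged by group. With "Group 1, Continuous Ambulation (n = 12), and Group 2, Interval Ambulation (n =10", judging each group would require 10 of 12 and 9 of 10, which is stricter; pooling is used here.

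**Assumptions.** Let s be per-exit sensitivity and k the exits per observational badge. Neither k nor the number of HIIT crossings is in the documents. I take k from 1 to 4, one exit per HIIT session, and independent detection.

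**One-detection reading.** A badge passes with probability q = 1 − (1 − s)^k. The observational cohort passes with P(X ≥ 33), X ~ Bin(40, q). HIIT passes with P(X ≥ 18), X ~ Bin(22, s).

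| s | Obs. k=1 | k=2 | k=3 | k=4 | HIIT |
|---|---|---|---|---|---|
| 0.45 | <0.001 | 0.05 | 0.66 | 0.97 | 0.0005 |
| 0.50 | <0.001 | 0.18 | 0.88 | 0.997 | 0.002 |
| 0.70 | 0.06 | 0.98 | >0.999 | >0.999 | 0.16 |
| 0.90 | 0.96 | >0.999 | >0.999 | >0.999 | 0.94 |
| 0.95 | 0.999 | >0.999 | >0.999 | >0.999 | 0.996 |

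For example, at s = 0.70 and k = 2, q = 1 − 0.3² = 0.91. At s = 0.50 and k = 3, q = 1 − 0.5³ = 0.875. With one exit per badge the two rules are about equally hard: an 80% chance of passing needs s = 0.858 (observational) or 0.856 (HIIT).

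**Correlated misses.** Use a beta-binomial with within-badge correlation 0.3, so a = s × 0.7/0.3 and b = (1 − s) × 0.7/0.3.

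- s = 0.45, k = 3: q falls from 0.834 to 0.715, and the pass probability from 0.66 to 0.08.
- s = 0.50, k = 3: from 0.88 to 0.23.
- s = 0.70, k = 2: a = 1.633, b = 0.7, P(no detection) = (0.7 × 1.7)/(2.333 × 3.333) = 0.153, so q = 0.847 and the pass probability falls from 0.98 to 0.74.

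**Patients who never leave the room.** If 10% of observational patients never exit:

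- s = 0.45, k = 3: q = 0.9 × 0.834 = 0.750, pass probability 0.18.
- s = 0.70, k = 2: q = 0.9 × 0.91 = 0.819, pass probability 0.56.

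**Every-exit reading.** If a badge must catch all its exits, q = s^k. At s = 0.9 and k = 3, q = 0.729 and the observational cohort passes with probability 0.11, against 0.94 for HIIT. The order reverses.

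**The case against.** The strongest reply is that this is a descriptive pilot. The primary outcome asks whether the system can detect movement in and out of a room, which a presence-or-absence rule fits. Sensitivity would be reported anyway, so a poor value would be visible, and no comparison of the two cohorts' percentages is planned. Section 7.1 also reports near-perfect sensitivity in controlled tests, where both rules pass almost surely.

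Much of this stands as a limit on size, and several stronger readings that a reader might infer are not supported:

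- That the plan accepts one detection. It does not say so. This is the minimal literal reading; an every-exit reading is also open.
- That observational badges have at least three chances. Three visit days is a maximum, walks can be refused, and the background section reports little movement in earlier patients, though possibly as a device artifact.
- That a system missing most exits would be declared feasible. That needs about 3 to 4 or more independent exits per badge. Section 7.1 names badge positioning as a possible cause of lost sensitivity; such a cause may persist within a badge and so correlate its misses.
- That HIIT is always far harder to pass. At high sensitivity, or with one exit per observational badge, it is not.

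The reply does not remove the defect. Reported sensitivity has no role in the feasibility decision, section 1.0 calls the system's reliability unknown, and section 7.1 itself warns that sensitivity may fall in use. A feasibility rule has to discriminate in that range.

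**Conclusion.** The concern holds in a limited form. The sole feasibility criterion leaves per-badge success undefined, and the result can turn on that unwritten choice. On the minimal reading, the observational rule can pass a system of only moderate per-exit sensitivity, while the same system would probably fail in HIIT: 0.98 versus 0.16 at sensitivity 0.70 with 2 exits, 0.88 versus 0.002 at 0.50 with 3 exits, and 0.66 versus 0.0005 at 0.45 with 3 exits.

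These figures rest on independent detection, every observational patient leaving the room, and one exit per HIIT session, none of which the documents establish. The result at 0.45 is fragile, falling to 0.08 or 0.18 under the two departures examined. The result at 0.70 is less so, at 0.74 or 0.56. At 0.95 the gap is negligible (above 0.999 versus 0.996). The documents support saying that the rule can mislead, not that it will.

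**What to change.** In section 7.2:

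1. Base the feasibility conclusion in both cohorts on exit-level sensitivity: of the staff-timed walks that left the room, the proportion for which the badge log shows both the exit and the return. Use all such walks, not a chosen one.
2. Give a confidence interval clustered by patient and read it against the 80% mark. State beforehand whether the estimate or the lower limit must exceed it.
3. Keep the percentage of assigned badges with a detection as a descriptive result, with all assigned badges in the denominator. Report how many badges had no out-of-room staff-timed walk, including HIIT patients who used only the hand bike.
4. State that an ever-detected percentage from the observational cohort is not to be compared with the HIIT percentage.
5. Label the observational analysis as specified after that cohort closed to enrolment.

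**Cost.** No new patients are needed. Section 5.6 already has staff record when each observational walk took place, its length and its duration, but does not say that leaving the room is recorded, so this must be established from those records. For HIIT, staff should note the clock time and whether the walk left the room. Walk records must be matched to the badge log, and the stated success percentage may be less favourable.
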